Précis: Of the over one million annual AHF hospitalizations, approximately 80% are initially treated in the emergency department (ED).^{1,2} AHF is the most common and costliest reason why patients over the age of 65 are hospitalized.³ While some clearly require admission, others do not.^{4,5} There is a spectrum of risk for ED patients with AHF. Previous reports suggest 50% of patients could be discharged from the ED or observed for less than 24 hours.⁴ Yet admission rates from the ED for AHF remain around 80%.⁶ From a patient perspective, we know patients and caregivers would prefer to spend as little time as safely possible in the hospital

Using a multi-center, randomized controlled design, this clinical effectiveness trial will test whether Short Stay Unit AHF management for < 24 hours increases DAOOH and QoL compared to usual care, defined as in-hospital management.

Objectives:

Aim 1: To demonstrate the effectiveness of a SSU AHF management strategy vs. usual AHF care (i.e. inpatient admission), using a randomized, controlled, simple, trial design.

Aim 2: To demonstrate that a SSU AHF strategy of care leads to equivalent or improved adherence to HF guidelines at time of discharge vs. usual care (i.e. hospitalization).

Endpoints

Primary Endpoint: Days alive and out of hospital at 30 days post-discharge.

Secondary Endpoints: 1) Quality of life as measured by Kansas City Cardiomyopathy Questionnaire 2) Cost-effectiveness analysis between the two arms at 30 days

Exploratory Endpoints:

1) Caregiver burden as measured by two Caregiver Burden Scales at 30 days; 2) Cost-Effectiveness of the SSU AHF strategy of care at 90 days; 3) Resource utilization measured by the Modified Resource Utilization Questionnaire for Heart Failure (mRUQ-HF) at 90 days 4) All cause mortality and re-hospitalization at 30 and 90 days 5) Days alive and out of hospital at 90 days 6) HF Guideline adherence at time of discharge

Population:

ED patients with AHF who meet inclusion and no exclusion criteria will be enrolled once written informed consent is obtained.

Phase:

NA

Number of Sites

Four. Projected sample size, n=534.

enrolling participants:

SSU AHF care for < 24 hours vs. usual care (inpatient admission) in ED patients with AHF who lack baseline high-risk features.

[figure not shown]
Description of Study

4.5 years. There will be three months of start up, and three months of study conclusion work. Enrollment will occur over 48 months.

Agent:**Study Duration:**

90 days post discharge

Figure 2: Patient Flow

2 INTRODUCTION: BACKGROUND INFORMATION AND SCIENTIFIC RATIONALE

2.1 BACKGROUND INFORMATION

Heart failure is a major public health burden. Over 5.5 million Americans have heart failure (HF), with 870,000 new diagnoses each year.³⁰ Within 5 years, half of these patients will be dead.³⁰ By 2030, the prevalence of HF will increase 46% and HF costs will increase, from \$31 billion to \$70 billion.³¹ Hospitalization for AHF consumes the majority of these dollars.^{32,33} HF is the most common reason why patients over the age of 65 are hospitalized.³ Hospitalization is not benign, marking patients at greatest risk for adverse outcomes.^{33,34} Re-hospitalized patients are at even greater risk.³⁴ After hospitalization, patients enter a *vulnerable phase*.³⁵⁻³⁸ During this vulnerable phase, approximately 20% of hospitalized patients experience another medical adverse event.³⁵ Not only patients are affected; hospitalization/rehospitalization takes a toll upon families and caregivers.³⁵

The emergency department (ED) accounts for the majority of the one million hospitalizations for AHF annually. Approximately 80% of AHF admissions are initially treated in the ED.^{1,2} Unlike chronic HF, no AHF treatment definitively prolongs life or reduces the risk for re-hospitalization.³⁹ Clearly some patients require admission, however a large proportion do not require prolonged hospitalization.^{4,5} Many AHF patients have congestion secondary to worsening chronic HF. These patients receive IV diuretic therapy and little additional pharmacologic management, despite a median length of stay of 4.3 days.^{1,22,25,40-42} This is one reason institutions advocate for outpatient 'infusion centers' or 'diuretic clinics.'⁴³ Admitting and re-admitting lower risk AHF patients who don't need it may increase their risk for poor outcomes and decrease their quality of life. **Safe alternatives to hospitalization from the ED are needed.** A recent NHLBI working group identified alternatives to hospitalization from the ED as a high priority.¹⁵ The Institute of Medicine identified observation units as an opportunity to improve patient flow resource utilization.⁴⁴

2.2 RATIONALE

Small studies, retrospective analyses, and the Society for Cardiovascular Patient Care (SCPC; now American College of Cardiology [ACC] Accreditation Services) guidelines support brief observation (< 24 hours) or short stay unit (SSU) management of AHF to be effective for lower risk AHF patients. Our group's early work demonstrated lower overall median length-of-stay compared to a risk-matched inpatient only group (25.7 vs 58.5 hours).⁴⁵ Importantly, total charges were approximately \$3600 less for the SSU compared with those admitted from the ED. In a retrospective study of 358 patients using SCPC guidelines, the authors observed less hospital bed day utilization and similar 30-day readmission rates (12.5% vs 10.0%), respectively after adjustment for age, race, sex, BNP, renal function and ejection fraction.⁴⁶ SSU discharges spent 2.4 days and 2.5 days within 30 and 90 days of follow-up, respectively, compared with 4.4 and 5.0 days among patients admitted to the hospital after SSU management ($p<0.0001$).⁴⁶ Those patients who weren't ready for discharge after SSU management were admitted to the hospital for further treatment. **However, several knowledge gaps hinder broad uptake of SSU management.** First, an adequately powered, randomized controlled trial of SSU AHF care has not yet been conducted. Second, the impact of a SSU AHF strategy on quality of life and caregiver burden is unknown. Third, due to reimbursement differences, patients may face increased out-of-pocket costs. Finally, clinicians and caregivers may think SSU is just 'gaming the system' to avoid readmission penalties. We address each of these gaps in our proposal.

2.3 POTENTIAL RISKS AND BENEFITS

2.3.1 KNOWN POTENTIAL RISKS

Patients will only receive current usual care for acute heart failure. There will be no experimental drugs or therapies. However, the SSU will receive protocolized care while the usual care arm will receive the non-protocolized AHF care per routine. Past small studies and retrospective analyses demonstrate the safety and efficacy of SSU management. Furthermore, if SSU treated patients are not ready for discharge, they will be admitted. Thus, there is a built in 'safety-net.' However, the SSU strategy has not been tested in a randomized, controlled, clinical trial. Nevertheless, there is a risk that patients will be discharged prematurely from either setting.

2.3.2 KNOWN POTENTIAL BENEFITS

Patients enrolled in this study who are receiving the strategy-of-care or usual care may receive a benefit such as decreased mortality, or less frequent hospitalizations related to HF, or leave the hospital sooner, or improved quality of life. If this study is positive, future patients may benefit from avoiding unnecessary time in the hospital, but equal or better outcomes.

3 OBJECTIVES AND PURPOSE

Objectives:

1: To demonstrate the effectiveness of a SSU AHF management strategy vs. usual AHF care (i.e. inpatient admission), using a randomized, controlled, simple, trial design.

2. To demonstrate that a SSU AHF strategy of care leads to equivalent or improved adherence to HF guidelines at time of discharge vs. usual care (i.e. hospitalization).

Purpose:

The overarching goal of this comparative effectiveness study is to increase days-alive-and-out-of-the-hospital (DAOOH) and improve quality of life (QoL) for lower risk AHF patients who present to the emergency department (ED). We hypothesize an alternative to hospitalization, SSU AHF management of less than 24 hours, will achieve our goal.

4 STUDY DESIGN AND ENDPOINTS

4.1 DESCRIPTION OF THE STUDY DESIGN

A prospective, randomized, controlled, simple, comparative effectiveness study of a strategy of care (SSU care) vs. usual care (inpatient admission) in ED patients with AHF who lack baseline high-risk features and ineligible for ED discharge.

4.2.1 PRIMARY ENDPOINT

Days alive and out of hospital at 30 days post-discharge.

4.2.2 SECONDARY ENDPOINTS

1) Quality of life as measured by Kansas City Cardiomyopathy Questionnaire 2) Cost effectiveness analysis between the two arms at 30 days.

4.2.3 EXPLORATORY ENDPOINTS

1) Caregiver burden as measured by **Oberst Caregiving Burden Scale and Bakas Caregiving Outcomes Scale** ; 2) Cost-Effectiveness of the SSU AHF strategy of care at 90 days; 3) Resource utilization measured by the Modified Resource Utilization Questionnaire for Heart Failure (mRUQ-HF) 4) All cause mortality at 30 and 90 days 5) All cause re-hospitalization at 30 and 90 days; 6) Days alive and out of hospital at 90 days 7) HF Guideline adherence at 30 days

5 STUDY ENROLLMENT AND WITHDRAWAL

5.1 PARTICIPANT INCLUSION CRITERIA

- 1) ED physician clinical diagnosis of AHF;
- 2) Planned admission for AHF
- 3) Systolic blood pressure > 100mmHg*, heart rate < 115bpm. The last HR and SBP should be within 1 hour of randomization.
- 4) Previous history of HF

*Patients with atrial fibrillation but controlled HR are eligible

For Caregiver Burden assessments. The eligibility criteria for a caregiver: 1) person either self-identifies, or when asked identifies themselves, as the primary caregiver for the patient. If there are multiple caregivers, the person who self-identifies as providing the most care will be asked to provide verbal informed consent. This part of the investigation poses no more than minimal risk to the subject and caregivers will be provided with information about the study and the processes for the initial and 30 day follow up questionnaires. For patients with no caregiver identified, no caregiver assessment will be performed.

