7.3.7 SCHEDULE OF EVENTS TABLE

Schedule of Events Timepoint/Visit	Screen	Baseline	ARM 1 - PreDischarge from SSU	ARM 2 - PreDischarge from Hospital Floor	30-Day & 90 Day Follow up
Informed Consent	X				
Medical History		X			
Physical Exam		X	X	X	
Clinical lab tests*		X	X~	X~	
ECG*		X			
CXR*		X			
KCCQ (QoL) & SF-12			X	X	X
Oberst Caregiving Burden Scale and Bakas Caregiving Outcomes Scale			X	X	X ¹
HF Guideline Assessment			X	X	
Collect concomitant meds		X	X	X	
mRUQ-HF (resource utilization)					X ²
Cost Effectiveness Measures (i.e. DRG)					X
Guideline adherence assessment		X	X	X	X ¹
SCPC Discharge Criteria Adherence			X	X	
Assessment of AE/SAE's through 5 days			X	X	
Vital Status, ED visits, Hospital days, Re-admission status			X	X	X
Subject Payment			X	X	X ²

*per standard of care. Typical labs include: Na, K, renal function, HgB, troponin, Natriuretic Peptide levels. ~only if performed per usual care

SOC = standard of care, ED = Emergency Department, QoL = quality of life, HF = heart failure, mRUQ = modified resource utilization questionnaire, EMR = electronic medical record, DRG = diagnosis related group

¹Only through 30 days

²Sites may choose to make a single payment or to divide into 2 payments.

³only at 90 days

NOTE: If patients are hospitalized from the SSU, ONLY the following assessments should be collected. Otherwise, the pre-discharge assessments will apply.

- Physical exam
- Clinical lab tests
- Con meds
- SCPC discharge criteria. This would be conducted twice. Once in SCPS prior to hospitalization and again at discharge.

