Decreasing hospital stays may increase caregiver burden. Thus, we will also assess caregiver burden, using both the Oberst Caregiver Burden and Bakas Caregiver Outcome Scales, both validated instruments prior to discharge and again at 30 days.⁶⁸ Other measures of caregiver burden in HF have either not involved input from actual caregivers or missed important conceptual domains.⁶⁸ Effective caregivers has been associated with improved quality of life, lower hospitalization rates, and reduced mortality.^{68,69} As our primary focus is on the patient, the eligibility criteria for the caregiver will be broad, essentially including any person who after separate written informed consent, acknowledges themselves as the primary caregiver for the patient.

Out-of-pocket costs directly impact patients. As such, we will assess healthcare utilization from a societal perspective using the Modified Resource Utilization Questionnaire for Heart Failure (mRUQ-HF).⁷⁰ The mRUQ-HF is a 14-item self-report questionnaire of comprehensive lists of choice related to healthcare utilization. (See Appendix trial protocol) Exploratory analysis will occur in two steps: 1) Determination of resources consumed or related; 2) Assignment of 'value' to the resources consumed.⁷¹ This two-step process allows for transparency of assigned costs. Hospital costs will be assigned per individual hospital cost-accounting. Where monetary values are not directly self-reported, Medicare fee schedules will be used for uniformity.

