10.6 MEASURES TO MINIMIZE BIAS

10.6.1 ENROLLMENT/ RANDOMIZATION/ MASKING PROCEDURES

Patients will be randomized 1:1 to one of the two study arms, but stratified by site to ensure equal site representation. A central computer generated randomization scheme with random block sizes of two, four, and six will be created, stratified by site. The REDCap randomization module will be utilized to generate the randomization schema and patient allocation.

Due the nature of the intervention and the clinical setting, this is an unblinded trial.

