 A moderate amount (3)	Moderately difficult (3)
 A small amount (2)	Slightly difficult (2)
 None (1)	Not difficult (1)

About how many hours/day

About how many hours/week

16. Seeking information and talking with doctors, nurses, and other professional health care workers about the patient's condition and treatment plans:

Time you spend:

- A great amount (5)
- A large amount (4)
- A moderate amount (3)
- A small amount (2)
- None (1)

How difficult:

- Extremely difficult (5)
- Very difficult (4)
- Moderately difficult (3)
- Slightly difficult (2)
- Not difficult (1)

About how many hours/day

About how many hours/week

Bakas Caregiving Outcomes Scale (BCOS)

Site Specific ID or MRN

Page 1 of 2

Was a caregiver identified? Defined as person either self-identifies, or when asked identifies themselves, as the primary caregiver for the patient.

No

Yes

Person who filled out form

Caregiver filled out the form

Research staff Asked the caregiver in person

Research staff Asked the caregiver by phone

This group of questions is about the possible changes in your life from providing care for your family member or loved one. For each possible change listed, circle one number indicating the degree of change. The numbers indicating the degree of change range from 3 Changed for the Worst to +3 Changed for the Best. The number 0 means Did Not Change.

1. My self esteem
2. My physical health
3. My time for family activities
4. My ability to cope with stress
5. My relationship with friends
6. My future outlook
7. My level of energy

8. My emotional well-being
9. My roles in life
10. My time for social activities with friends

-3 Changed for the Worst

-2 -1 0 Did Not Change

1 2 3 Changed for the Best

11. My relationship with my family

12. My financial well-being

13. My relationship with the heart failure patient

14. My physical functioning

15. My general health

16. In general, how has your life changed as a result of taking care of the heart failure patient?

If there any other changes in your life as a result of providing care, please write them below and rate them accordingly.

17 Description

Confidential

Page 2 of 2

17 Rating

-3 Changed for the Worst

-2

-1

0 Did Not Change 1

2

3 Changed for the Best

18 Description

18 Rating

-3 Changed for the Worst

-2

-1

0 Did Not Change 1

2

3 Changed for the Best

19 Description

19 Rating

-3 Changed for the Worst

-2

-1

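### The plan does not require caregivers to be identified before randomization, so the caregivers analysed for burden may be selected differently by arm

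*Combined protocol and SAP*

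**What the plan says.** Section 5.1 makes a caregiver eligible when the "person either self-identifies, or when asked identifies themselves, as the primary caregiver for the patient". It gives no time at which this is established. It then states: "For patients with no caregiver identified, no caregiver assessment will be performed".

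Randomization takes place during the ED stay (7.3.1), and 10.6.1 confirms that "this is an unblinded trial". Neither the screening list in 7.3.1 nor the enrollment text in 7.3.2 contains a caregiver step.

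In the schedule (7.3.7), the row for the "Oberst Caregiving Burden Scale and Bakas Caregiving Outcomes Scale" is blank under Screen and Baseline. Its first marks are in the two arm-specific pre-discharge columns. Section 10.1.1 agrees, placing "both validated instruments prior to discharge and again at 30 days". The item "Was a caregiver identified" stands on the Bakas form in 17.2, which follows that schedule.

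For the analysis, 10.4.3.1 says only that caregiver burden is handled like the KCCQ, and it gives a table of detectable effects by attrition. Caregiver burden is an exploratory endpoint (4.2.3) that also enters the cost-effectiveness work (10.4.3).

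**The concern.** Section 10.1.1 recognises that shorter stays might shift burden onto caregivers and uses these scales to look for it. The comparison is thus the plan's check on a possible harm of the SSU strategy, and 5.3 treats completion of these questionnaires as critical to the study.

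Randomization protects a comparison when membership of the analysed set is settled before allocation or cannot be affected by it. Here membership can be settled afterwards, by staff who know the arm, over a stay whose planned length depends on the arm. If a longer stay makes it easier to find a less involved caregiver, the usual-care group would contain caregivers whose counterparts in the SSU arm were never counted. A burden difference could then appear, or a real one be hidden, because of who was found.

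The rest of the plan does not repair this. Multiple imputation under missing at random (10.4.5) does not reach patients recorded as having no caregiver, because they are never assessed. The attrition table treats missing caregivers only as lost power. No pre-randomization burden score exists to adjust for.

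**Working it through.** **1. The plan's own table.** Detectable effect at 80% power, two-sided 0.05, SD = 1: (1.960 + 0.842) × √(2/n), n per arm.

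| Total N | Attrition, 1 − N/534 | Computed effect | Plan |
|---|---|---|---|
| 480 | 10.1% | 0.256 | 0.25 |
| 360 | 32.6% | 0.295 | 0.30 |
| 240 | 55.1% | 0.362 | 0.37 |
| 120 | 77.5% | 0.512 | 0.51 |

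The table reproduces within rounding. It concerns numbers only and says nothing about which caregivers are analysed.

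**2. The time available in each arm.**
- SSU stay: under 24 hours (6.1.1), but 10.5 assumes 40% of the arm is admitted.
- Usual care: cited median 4.3 days (6.1.1). The risk-matched pilot in 2.2 had 58.5 hours, or 58.5/24 = 2.4 days, against 25.7 hours for the SSU group.

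The planned windows differ, by an amount that depends on which source is used.

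**3. Possible bias with no true effect.** The documents give no identification rates, so every input in this step is an assumption.

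*Model A.* Let pC and pS be the shares of randomized patients with an identified caregiver in usual care and SSU. The share of usual-care caregivers who would not have been found under SSU is f = (pC − pS)/pC. If their burden differs by d SD from the others, bias = f × d.

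| pC vs pS | f | d = 0.25 | d = 0.5 | d = 1.0 |
|---|---|---|---|---|
| 90% vs 85% | 0.056 | 0.01 | 0.03 | 0.06 |
| 80% vs 70% | 0.125 | 0.03 | 0.06 | 0.13 |
| 70% vs 60% | 0.143 | 0.04 | 0.07 | 0.14 |
| 70% vs 50% | 0.286 | 0.07 | 0.14 | 0.29 |
| 60% vs 40% | 0.333 | 0.08 | 0.17 | 0.33 |

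With 267 × p × 0.9 responding caregivers per arm (90% response assumed), the chance that a nominal 5% test rejects runs from 5% to 72% over this grid. That spread is too wide for any one figure to be informative.

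*Model B.* The most involved caregivers are found first, and involvement correlates r = 0.3 to 0.5 with burden. The mean involvement of the top fraction p of a standard normal is φ(z)/p: 0.798 at p = 0.50, 0.644 at 0.60 and 0.424 at 0.75. Here p is the share identified among patients who have a caregiver.
- 50% (SSU) vs 75%: difference 0.374, so bias is 0.11 (r = 0.3) to 0.19 SD (r = 0.5).
- 60% vs 75%: difference 0.220, so bias is 0.07 to 0.11 SD.

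**4. Effect of SSU admissions.** Suppose the 40% admitted are identified at the usual-care rate of 75% and the rest at 50%. The SSU rate is 0.6 × 0.50 + 0.4 × 0.75 = 0.60. Mean involvement in that arm is (0.30 × 0.798 + 0.30 × 0.424)/0.60 = 0.611. The difference from usual care is 0.611 − 0.424 = 0.187, and the bias is 0.06 to 0.09 SD. Admissions dilute the bias but do not remove it.

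**The case against.** The strongest objection is that the timing is inferred. A reader might take the schedule to mean that caregivers are in fact first identified at the pre-discharge assessment. The documents do not say so. The schedule times the questionnaires, while caregiver eligibility sits in 5.1 with no time attached. Identification in the ED is compatible with the text. So is identification by phone, which the Bakas form allows, or at the 30-day contact, which is timed from discharge in both arms. This stands, and the point is therefore limited to what the plan fails to require.

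Second, the mechanism may be weak. The criterion is the primary caregiver or, if there are several, the one giving most care. It does not depend on visiting the ward, and phone contact reduces any advantage of a longer stay.

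Third, allocation does not fully set the stay. Both arms continue until the patient is ready for discharge (6.1.2), 40% of SSU patients are assumed admitted, and 10.4.3.1 monitors usual-care discharges within 48 hours. The schedule's note on patients hospitalized from the SSU omits the caregiver scales at that step, so these patients would apparently be assessed at hospital discharge. The note's scope is unclear. As step 4 shows, this reduces the bias.

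Fourth, 10.4.3.1 monitors questionnaire response and completeness, with reports every three months to the Steering Committee and at enrollment milestones to the DSMB. This could reveal a large imbalance, but it neither defines the analysis set nor prevents selection.

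Finally, the endpoint is exploratory, and Model B's largest bias (0.19 SD) is below the smallest effect in the plan's table (0.25 SD). Both statements are correct, and they keep the point modest.

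**Conclusion.** The point holds in a limited form. The plan lets entry to the caregiver set be settled after open allocation, over planned stays that differ by arm, and it has no provision that corrects for this. The caregivers analysed may be selected differently, so randomization does not fully protect the comparison.

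The size is unknown. Under the assumed inputs, bias runs from about 0.01 SD with a small gap in identification to about 0.1 to 0.2 SD with moderate or larger gaps. It exceeds that only where rates differ by 20 percentage points and the extra caregivers differ strongly in burden. These figures rest wholly on assumed identification rates and on an assumed link between being found and burden.

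Two stronger conclusions might be drawn. One is that the arms are in fact differently selected; without identification rates by arm, the documents support only that they may be. The other is a specific inflated false-positive rate, which would merely restate the chosen assumptions. The primary endpoint is not affected. This is an inexpensive improvement to an exploratory comparison that bears on a possible harm and feeds the secondary cost-effectiveness analysis.

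**What to change.** - **5.1 and 7.3.1:** at consent in the ED, before randomization, ask the patient whether there is a primary caregiver and who it is. Record the answer as a baseline item.
- **7.3.7:** mark caregiver identification under Screen/Baseline.
- **10.4.3.1:** define the main caregiver-burden set as patients with a caregiver named before randomization, analysed as randomized, with phone completion allowed. Report identification and questionnaire response by arm out of all randomized patients. Include caregivers first found later only in a sensitivity analysis.

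The cost is one screening question, one schedule entry and a short addition to the analysis section. Some named caregivers will not respond and will become visible missing data with a known denominator. Response could still differ by arm. Caregivers found later leave the main analysis.

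Assuming 90% response, the formula in step 1 gives detectable effects of 0.27 SD if 90% of patients name a caregiver (534 × 0.9 × 0.9 ≈ 433 analysed), 0.31 SD at 70% (336) and 0.36 SD at 50% (240).

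Separately, caregiver consent is verbal in 5.1 ("the person who self-identifies as providing the most care will be asked to provide verbal informed consent") but written in 10.1.1 ("essentially including any person who after separate written informed consent, acknowledges themselves as the primary caregiver for the patient"). These passages should be reconciled. Neither gives a time, and the present point stands under either form of consent.
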